Modern intensive care enables patients to survive insults that in the past would not have been survivable. Nonetheless, increased number of survivors suffer from failed functional outcomes associated with prolonged muscle weakness and fatigability. Whilst alterations of skeletal muscle biology that occur during critical illness slowly disappear over the period of months, muscle weakness remains. Recent pilot studies have shown that muscle weakness is associated with loss and alteration of satellite skeletal muscle cells, which are supposed to proliferate and repair damaged muscle tissue. The pathogenesis of this phenomenon has not been fully understood. In this project, we will study function and structure of satellite cells and their organelles (particularly mitochondria) using both classical bioenergetics and advanced microscopic techniques. Satellite cells will be isolated from biopsies taken from critically ill patients with developed muscle weakness in the acute and protracted phase of a disease and after 6 months. In time points, an ultrasound examination of muscle mass will be performed, and metabolism will be assessed using insulin clamps and calorimetry. In a series of in vitro experiments, we will test also effect of nutritional and anabolic factors and drugs, commonly used in ICU, on satellite cells. In a control arm, cells will be isolated from skeletal muscle of volunteers undergoing elective hip replacement surgery. Results of this study could significantly contribute to understanding of mechanisms leading to ICU acquired muscle weakness and to identify therapeutic strategy in future.

Key words: intensive care unit-acquired weakness; critically ill; skeletal muscle regeneration; satellite cells

BACKGROUND

Skeletal muscle weakness is a frequent complication of critical illness associated with an increased morbidity and mortality [1]. Altered muscle strength and functional ability occur mostly in patients with sepsis or extensive inflammatory response who require prolonged duration of mechanical ventilation and hospital stay[2]. In patients surviving intensive care, muscle weakness remains a long-term complication leading to significantly decreased quality of life[3,4]. The mechanisms underlying this phenomenon have been extensively studied in both animal models and critically ill patients. Proteolytic muscle degradation, electrical alterations, and excitation-contraction decoupling are well known factors contributing to development of muscle weakness in the acute phase[5]. Even more importantly, recent studies have shown that failed long-term functional outcome in critically ill is associated with decreased satellite cell content[5]. Satellite cells are localized beneath the basal lamina surrounding each multinucleated myofiber[6]. In adult muscle, satellite cells are normally quiescent, but they can be recruited rapidly after a muscle damage, providing the muscle with an ability to regenerate[7]. During injury, satellite cells are activated from the quiescent state (G0 phase) and enter the cell cycle (G1 phase)[8]. Most activated satellite cells then proliferate and are referred to as “myoblasts”. Myoblasts subsequently differentiate and express myogenic factor which allows them to fuse between themselves into multinuclear cylindrical myotubes and with the existing fibres to regenerate the damaged muscle tissue[6,8]. Some satellite cells return to the G0 state to replenish the pool of quiescent skeletal muscle cells[6,8]. These processes are regulated by key transcriptional factors such as Pax7 and myogenic regulatory factors[9,10]. Myotubes are highly metabolically active, rely on oxidative phosphorylation in a rich population of mitochondria which are structured in organized networks[11]. In contrast, myoblasts are more dependent on glycolysis and contain less mitochondria. Shortly after muscle injury, myogenic differentiation occurs[11] and mitochondrial mass, protein content and number of mitochondrial DNA copy increase[12,13]. Moreover, recent studies have shown that shape of mitochondria is also remodelled during myogenic differentiation[14,15]. Mitochondrial morphology is controlled by balanced processes of fusion and fission machinery[15,16]. Balanced fusion and fission events shape mitochondria to meet metabolic cues and to ensure removal of damaged organelles[16]. Mitochondrial morphology is therefore dramatically changed in response to various metabolic inputs[16] and it is tightly

regulated[15,16]. The morphology of mitochondria is altered in disease: mitochondria can shape into elongated tubules during mild stress and starvation. In contrast, acute severe stress frequently causes a dramatic mitochondrial fragmentation and decreased oxidative phosphorylation[16].

Recent studies performed on animal models have shown that some of the proteins responsible for the processes of fusion and fission are crucial for the proper muscle growth and function of mitochondria in muscle cells[15]. Therefore, alterations in mitochondrial dynamics often play a crucial role in skeletal muscle dysfunction and have been recently extensively studied in several myopathies[17]. Although it has been established that skeletal muscle regeneration parallels altered mitochondrial dynamics and biogenesis, the cells that mediate the remodelling of mitochondrial networks have not been yet thoroughly investigated[18]. Moreover, there is still lack of clear information about mitochondrial dysfunction in skeletal muscle weakness after critical illness.

Our group already adopted a method of satellite cell isolation and culture from human vastus lateralis biopsies and tested nutritional influences[19]. We have found in a pilot experiment that bioenergetic profiles of myotubes from patients with protracted ICU stay differ from healthy control, mostly by mitochondrial mass deficiency and reliance of remaining mitochondria on lipid-derived substrates[20]. In addition, we found out that 4 days of propofol exposure induces respiratory chain alterations (mostly fatty acid oxidation defect)[21], which we later managed to further characterize [22]. Long term significance of these findings to satellite cell ability to repair damaged muscle remains unknown.

STUDY HYPOTHESES AND AIMS

Hypothesis:

Critical illness induces damage to satellite cells in skeletal muscle that later impairs skeletal muscle structural and functional recovery and contributes to persistent weakness and failed functional outcome.

Aims of the project:

1. We will compare structural and functional (incl. bioenergetic) characteristics of satellite cells in acute, protracted and post-ICU phase in critically ill patients vs. control subjects.
2. We will test the hypothesis that structural and/or functional alteration of satellite cells correlate with gross muscle mass and power in survivors of critical illness.
3. We will elucidate factors that influence bioenergetics and mitochondrial morphology of satellite cells (such as extracellular inflammatory milieu, drugs common in ICU as well as nutritional and anabolic factors).

METHODS

General methodological approaches

1. Clinical outcomes will be assessed by objective validated tests such as SF-36 questionnaire for the quality of life assessment, Medical Research Council Score of muscle power and 6 minutes walking test to measure aerobic performance.
2. Metabolic characteristics will be assessed at whole body level by hyperinsulinaemic euglycaemic clamps and at tissue level by vastus lateralis biopsies.
3. We will assess global mitochondrial indices of satellite cells by oxygen consumption measurement (production of ATP, uncoupling of inner mitochondrial membrane, maximal respiratory capacity of respiratory chain, glycolytic capacity and fatty acid oxidation). Simultaneously, we will measure production of reactive oxygen species and mitochondrial membrane potential. The changes will be assessed in various time intervals in the acute, protracted and post-ICU phase of critical illness.
4. We will analyze mitochondrial density, structure and organization of mitochondrial network in satellite cells, length of mitochondrial branches and connections in the acute, protracted and post-ICU phase of critical illness.

Design

Investigator initiated, prospective, controlled, cohort study with physiological end-points

Study subjects

Inclusion Criteria: All of the following must be present:

- Critically ill patients receiving mechanical ventilation, to be enrolled within 72 hours of admission, who are likely to need 7 days or more of ICU stay
- Sudden onset of disease, which can be determined in time (such as trauma, stroke, sudden cardiac arrest etc.)
- Informed consent signed by patient or patient's representative

Exclusion criteria: None of these shall be present

- Unlikely to survive 6 months
- Premorbid downslope functional trajectory or poor performance status (ECOG Gr. 3 or worse) or baseline functional status unknown
- Bleeding disorder (INR \geq 1.5 or PLT $<$ that would preclude muscle biopsies)
- Known mitochondrial disease
- Endocrine crisis as a reason for admission
- Pregnant women

Control subjects: Elective hip surgery patients with very good to excellent performance status, only limited to joint pain (ECOG 0)

Informed consent procedure

All patients with capacity will be asked to provide a prospective written informed consent (See Appendix 3). For patients without capacity, a deferred consent procedure will take a place. In this case, an independent clinician will review and sign that the patient is lacking capacity and he/she fulfils all criteria to be enrolled to the study. The patient's next of kin will be informed about the study as soon as practical with the aid of information leaflet (Appendix 3). The patient will be asked to provide and sign informed consent as soon as he/she regains the capacity to do so. In case of consent refusal, patient's data will not be used in per-protocol analysis.

Study procedures

Eligible patients will be assessed at baseline, after 7 days and 6 months by clinical tests, metabolic tests and muscle biopsies as shown in table 1.

Test	Baseline	Day 7 or ICU discharge	6 months follow up	Note: Control subjects
Enrolment criteria, informed consent	x			x
Insulin clamps		x	x	x
Muscle biopsy	x	x	x	X
Functional performance test			x	x
Muscle mass by ultrasound	x	x	x	x

Table 1: Study procedures

Biopsies. Experimental group (= critically ill): Skeletal muscle samples (70 – 100 mg of muscle tissue) will be obtained from vastus lateralis muscle by needle biopsy technique (Bergström needle). *Control group (= orthopaedic patients):* Biopsies (> 100 mg of muscle tissue) will be taken from vastus lateralis muscle by open technique during surgery in control (hip replacement surgery)patients.

Isolation and cultivation of cells. Skeletal muscle cells will be isolated and cultured as previously described [19] (see **Figure 1**).

[figure not shown]

Figure 1. Primary human skeletal muscle cells. Myoblasts (A) and differentiated myotubes (B) under binocular inverse microscope and appearance of myoblasts (C) and myotubes (D) stained for desmin (AB 907 rabbit anti-desmin polyclonal antibody [Millipore, Billerica, MA, USA]) under confocal laser scanning microscopy. Source: published data of main proponent [19].

Bioenergetic profile. Mitochondrial metabolism will be assessed in living cells using Extracellular Flux Analyzer (Agilent Technologies Inc.) or high resolution respirometry (Oroboros O2k, Austria)[26], which simultaneously measures oxygen consumption rate (OCR) and extracellular acidification rate (ECAR) with oxygen-sensing fluorophores and pH sensors in a real time. The technology uses a piston to reversibly enclose a small volume above the microlayer of cells seeded in a multi-well plate. During the experiment, oxygen consumption rate (~respiration) and proton excretion (~glycolysis) cause rapid and easily measurable changes in dissolved oxygen concentration and free protons in the microchamber. The changes are monitored at the baseline of experiment and after addition of up to 4 test agents. The technology enables us to determine basal respiration, ATP production, proton leak, maximal respiratory capacity (see **Figure 2**) and glycolysis or respiration linked to individual complexes of respiratory chain. Fatty acid oxidation will be measured by Extracellular Flux Analysis and independently by another method of measurement of radioactively labelled [$1\text{-}^{14}\text{C}$] palmitate oxidation using liquid scintillation [21].

[figure not shown]

Figure 2. Principle of Extracellular Flux Analysis: oxygen consumption rate (OCR) measured at baseline and after addition of 1) oligomycin = ATP synthase inhibitor to distinguish ATP production and proton leak, 2) carbonyl cyanide-4-(trifluoromethoxy)phenylhydrazone (FCCP) to maximally stimulate respiratory chain and 3) antimycin A and rotenone (AA/rot) to inhibit respiratory chain. Experiments were performed on myoblasts isolated from skeletal muscle (m. vastus lateralis] from orthopedic patients (n = 8).

Source: main author's published data [19].

Mitochondrial structure and membrane potential measurement. In parallel with OCR and ECAR analysis, mitochondrial structure will be determined. These parameters will be visualized and quantified in living cells via fluorescent microscopic tools in high resolution using Confocal Laser Scanning Microscopy with a 63x oil immersion objective (Leica TCS SP5 system, Leica Microsystems). Measurement will be based on accumulation of fluorescent dye inside mitochondria (MitoTrackerTM Green staining) which enables to determine number and length of mitochondrial branches. Simultaneously, a positively charged dye tetramethylrhodamine ethyl ester will be used to image active mitochondria with excitation/emission maximum 549/575 nm[24]. Intensity of fluorescence will be normalized to levels measured after MitoTrackerTM Green staining (see **Figure 3**).

[figure not shown]

Figure 3. Satellite skeletal muscle cells after staining with MitoTrackerTM Green (MTG; left), tetramethylrhodamine ethyl ester (TMRE; in the middle) and after staining of both agents (right). Positively charged dye TMRE (mitochondrial membrane potential dependent) is accumulated only in active mitochondria due to its

relative negative charge. Determination of mitochondrial membrane potential is performed after normalization to MTG fluorescence (mitochondrial membrane potential independent), which covalently binds to mitochondrial proteins by reacting with cysteine residues.

Acquired data will be analyzed using ImageJ™ (MacBiophotonics).

Power analysis and statistical plan

There is no formal primary outcome and hence no formal power analysis can be performed. The so far largest trials in the field have both 11 subjects with complete follow up [5,27] and in our trial we will have at least twice this number. Comparison of morphological and functional indices between the elective hip surgery patients (control cohort) and critically ill patients upon ICU admission will be determined using a Welch's unpaired T-test. Changes of these parameters in time (ie. from ICU admission to 6 months following ICU discharge) will be determined using a linear mixed-effects model with random intercept.

Direct access to source data/documents

All study procedures will be properly recorded in accordance with the rules on medical records. The patient documentation shall include eligibility criteria, record of informed consent procedure and all relevant information obtained during subsequent visits. The documentation must be kept to allow for an additional assessment of possible early and late side effects of the method.

Quality control and quality assurance

To ensure compliance with Good Clinical Practices and all applicable regulatory requirement.

Ethical Considerations

The final study protocol, including the final version of the Informed Consent Form, must be approved or given a favourable opinion in writing by in the Ethics Committee (EC) as appropriate. The Investigator is also responsible for informing the EC of any amendment to the protocol in accordance with local requirements. The investigator is also responsible for providing the EC with reports of any serious side effect of study procedures.

The study will be performed in accordance with the protocol, ethical principles that have their origin in the Declaration of Helsinki WMA, and are consistent with Good Clinical Practice: Consolidated Guidelines and any applicable local regulation.

The Investigator(s) will ensure that subject (or the legal representative) is given full and adequate oral written information about the nature, purpose, possible risk and benefit of the study. Subject must also be notified that they are free to discontinue from the study any time. The subject (or the legal representative) should be given the opportunity to ask questions and allowed time to consider the information provided.

Voluntary written informed consent will be obtained before any study-related procedures are performed and the Investigator(s) must maintain the original, signed Informed Consent Form.

Data handling and recordkeeping

The team of investigators are allowed to inspect subject charts, study source documents, drug accountability records and other records relative to study conduct. The Investigator must maintain all documentation to the study for a period of 5 years after the end of last study subject.

Publication Policy

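### Aim 2 correlates satellite-cell alteration with the level of muscle mass and power in survivors, while the hypothesis is that earlier cell damage later impairs recovery; for muscle mass, the serial data to match the two are already scheduled

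*Protocol*

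**What the plan says.** The hypothesis (Protocol, Study hypotheses and aims) is ordered in time and concerns recovery: "Critical illness induces damage to satellite cells in skeletal muscle that later impairs skeletal muscle structural and functional recovery". It goes on to persistent weakness and failed functional outcome.

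Aim 2, in the same section, will test whether "structural and/or functional alteration of satellite cells correlate with gross muscle mass and power in survivors of critical illness". It does not say which biopsy supplies the cell measure, and it states the muscle outcome as a quantity in survivors, without reference to an earlier value. Aim 1 compares cells with those of controls by phase of illness. Aim 3 concerns factors that act on the cells.

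Under Study procedures, "Eligible patients will be assessed at baseline, after 7 days and 6 months by clinical tests, metabolic tests and muscle biopsies". In Table 1 the rows "Muscle biopsy" and "Muscle mass by ultrasound" are marked at all three patient visits and in controls. The row "Functional performance test" is marked in patients at 6 months only.

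Power analysis and statistical plan gives a Welch test of controls against patients at ICU admission, and a random-intercept mixed model for change in the morphological and functional indices over time. There is no formal primary outcome. On size, the largest earlier studies had 11 subjects with complete follow-up and "in our trial we will have at least twice this number".

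**The concern.** Recovery is a change within a patient after the insult. The level of muscle mass at follow-up also carries how much muscle that person had to begin with. On a level scale, a patient with small muscles who lost nothing can look the same as one with large muscles who lost half. Aim 2 as worded does not separate them.

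The direction of the association is also left open. If the 6-month biopsy is set against 6-month mass, wasted muscle yielding altered cells explains a correlation as well as damaged cells impairing recovery. Excluding the first explanation is the point of the hypothesis.

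What is at stake is interpretation. A positive result could be read as support for impaired recovery when it reflects body size. A null result could be read as evidence against the hypothesis when variation between people has diluted a real effect.

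**Working it through.** **Text side by side.**

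| Element | Hypothesis | Aim 2 |
|---|---|---|
| Cell measure | damage during critical illness | alteration, visit not stated |
| Muscle outcome | later recovery | mass and power in survivors |
| Own earlier value | implied by recovery | not mentioned |

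Neither analysis in the statistical section relates an earlier cell index to later muscle.

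**Inputs.** The protocol has no power figure to reproduce. Its minimum number of completers is 2 × 11 = 22. Two-sided alpha of 5% and every correlation below are assumptions.

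**Formulas.** Power = Φ(atanh(r) × √d − 1.96), with d = n − 3 = 19 for a simple correlation and d = n − 4 = 18 with one covariate. The partial correlation is (r − aρ)/√((1 − a²)(1 − ρ²)), where r is the raw correlation of cell index with 6-month mass, a is that of cell index with earlier mass, and ρ is that of earlier with 6-month mass.

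**Step 1. Effect of adjustment on detection, r = 0.40.** Unadjusted: atanh(0.40) × √19 = 1.847, so power is 45.5%.

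| a | ρ | Partial r | Power |
|---|---|---|---|
| 0 | 0.5 | 0.40/√0.75 = 0.462 | 56.4% |
| 0 | 0.7 | 0.40/√0.51 = 0.560 | 76.6% |
| 0.2 | 0.5 | 0.30/√(0.96 × 0.75) = 0.354 | 34.7% |
| 0.2 | 0.7 | 0.26/√(0.96 × 0.51) = 0.372 | 38.0% |
| 0.3 | 0.5 | 0.25/√(0.91 × 0.75) = 0.303 | 26.3% |
| 0.3 | 0.7 | 0.19/√(0.91 × 0.51) = 0.279 | 22.8% |

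Adjustment gains power when the cell index is unrelated to earlier mass. It loses power when part of the raw correlation came from earlier mass.

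**Step 2. Dilution.** Let early damage correlate 0.6 with change in mass, let damage and change both be unrelated to starting mass, and let k = SD of change / SD of starting mass. The correlation with the 6-month level is then 0.6k/√(1 + k²).

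| k | r with level | Power |
|---|---|---|
| 0.25 | 0.15 | 9% |
| 0.5 | 0.27 | 22% |
| 0.75 | 0.36 | 38% |
| 1.0 | 0.42 | 51% |

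The adjusted analysis has about 84% power throughout.

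**Step 3. False support.** Let there be no effect on recovery, but a correlation a between cell index and starting mass. The correlation with the 6-month level is a/√(1 + k²). For a = 0.3 it is 0.29 (k = 0.25) or 0.27 (k = 0.5); for a = 0.5 it is 0.49 or 0.45. At n = 22 this would be nominally significant about 22% to 64% of the time, although the correlation with change is zero.

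**The case against.** The strongest reply is that Aim 2 is silent rather than wrong. It fixes no cross-sectional analysis, alteration can mean change in the cells, and gross mass may simply mean whole muscle as opposed to cell. Visit, covariate and change score are often left to a statistical analysis plan, which is not at hand. The study is an exploratory cohort, and Aim 2 promises only a correlation.

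Much of this stands. A reader might infer that the protocol commits to a same-visit correlation, or that the serial ultrasound will go unused. The text supports neither: the biopsy visit is open, and nothing excludes the paired data from Aim 2. What remains is the outcome. However alteration is read, mass and power in survivors are levels, and an analysis plan that followed the aim faithfully would analyse levels. What the aim is meant to measure belongs in the aim.

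Four other tempting readings also fail:

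- That 6-month mass is mostly prior size. The documents give no figure. The assumed correlations of 0.5 and 0.7 correspond to 25% and 49% of variance.
- That adjustment always raises power. Step 1 shows that it can lower it.
- That adjusting for baseline mass isolates recovery. It combines ICU wasting with later regain. Nor is baseline premorbid mass: enrolment may be up to 72 hours after admission, so it is an early-illness value.
- That the whole of Aim 2 can be repaired with serial data. Patients have no functional test before 6 months, so power can only be a 6-month level, which is a reasonable outcome for persistent weakness.

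**Conclusion.** The point holds as a mismatch between hypothesis and aim. The hypothesis claims that damage "later impairs skeletal muscle structural and functional recovery and contributes to persistent weakness"; Aim 2 requires neither an earlier cell measure nor the patient's own earlier mass. A positive or null correlation would therefore leave the structural-recovery part of the hypothesis without a direct test.

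The conclusion rests on the wording and on Table 1, not on the power figures. Those illustrate the size under assumed correlations at the minimum of 22 completers: detection may rise from 45.5% to 56–77% or fall to about 23–26%. The case for change is mainly validity. Time order and adjustment bring the analysis closer to the hypothesis; they do not establish causation.

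**What to change.** Reword Aim 2 as follows.

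1. **Main analysis for ultrasound mass (recovery):** relate the cell index at day 7 or ICU discharge to 6-month mass, adjusted for the patient's own mass at that same visit.
2. **Second analysis (net loss since early illness):** relate the baseline cell index to 6-month mass, adjusted for baseline mass, noting that baseline is not a premorbid value.
3. **Power:** keep it as a 6-month level and say that no earlier functional test exists in patients.
4. **Same-visit 6-month correlations:** label them descriptive, not evidence that cell damage impairs recovery.

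This needs no new visit, biopsy or patient, because all the measurements are in Table 1. The cost is a change of wording and one degree of freedom per model, with possibly lower power if cell indices track earlier mass.

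### Does Aim 2 need a designated index and outcome, given that it speaks of testing a hypothesis while the protocol names no primary outcome?

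*Protocol*

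**What the plan says.** Aim 2 in the Protocol's section on hypotheses and aims reads: "We will test the hypothesis that structural and/or functional alteration of satellite cells correlate with gross muscle mass and power". It is restricted to survivors of critical illness.

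The section on general methodological approaches lists what will be measured in the cells. Item 3 gives the bioenergetic indices: "production of ATP, uncoupling of inner mitochondrial membrane, maximal respiratory capacity of respiratory chain, glycolytic capacity and fatty acid oxidation". It then adds that "we will measure production of reactive oxygen species and mitochondrial membrane potential". Item 4 gives the structural indices: "mitochondrial density, structure and organization of mitochondrial network in satellite cells, length of mitochondrial branches and connections". None is ranked above the others. On the clinical side, item 1 names the SF-36 questionnaire and the "Medical Research Council Score of muscle power and 6 minutes walking test to measure aerobic performance"; muscle mass is measured by ultrasound (Table 1).

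On timing, the study procedures state: "Eligible patients will be assessed at baseline, after 7 days and 6 months by clinical tests, metabolic tests and muscle biopsies". For patients, Table 1 places the functional performance test at 6 months only.

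The section on power and statistics says: "There is no formal primary outcome and hence no formal power analysis can be performed". The size is justified by comparison with the largest earlier studies, each with 11 completers: "in our trial we will have at least twice this number". It names two analyses, a Welch t-test against controls at ICU admission and a random-intercept mixed model over time.

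**The concern.** A stated hypothesis test normally has a designated result that decides it. Here the aim is phrased as a test, the alteration may be structural, functional or both, there are two outcomes, and no index or pair is singled out. A reader could fear that whichever index happened to correlate with mass or power would be presented as confirmation, with a false-positive risk well above the nominal level. Conversely, a single null correlation from about 22 patients would exclude little. The size statement does not help, because exceeding earlier studies does not show what the sample can resolve.

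**Working it through.** The protocol gives no significance level, power or effect size, so there is no stated figure to reproduce. Two-sided 5% and 80% power are assumed below for illustration only.

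**Inputs from the Protocol**
- Functional indices (item 3): 5 bioenergetic + reactive oxygen species + membrane potential = 7.
- Structural indices (item 4): 3 to 5, depending on how the joined terms are split.
- Total: 10 to 12; 11 is used here.
- Outcomes in Aim 2: 2 (mass and power).
- Completers: at least 2 × 11 = 22.

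**Number of correlations.** 11 × 2 = 22 at one visit (20 to 24 over the range of counts). The 6-month visit is the natural one, because the aim concerns survivors and patients have their functional test only then. No planned analysis relates the earlier biopsies to 6-month outcomes, so multiplying by three biopsies has no basis in the text.

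**Chance of at least one false positive, if every pair were tested at 5% and any positive counted**
- All tests independent: 1 − 0.95^22 = 0.68. This is a ceiling, not a realistic value: the indices share cells and assays, and mass and power are related.
- Simulated with n = 22, 100,000 draws, normal indices with equal pairwise correlation, unrelated to the outcomes, critical |r| = 0.423:

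| Mass–power correlation | Index correlation 0 | 0.5 | 0.8 |
|---|---|---|---|
| 0.5 | 0.65 | 0.50 | 0.32 |
| 0.8 | 0.60 | 0.44 | 0.27 |

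A separate run of 20,000 draws at mass–power correlation 0.5 gave 0.66, 0.51 and 0.31. The plausible range, with index correlation 0.5 to 0.8, is therefore about 27% to 50%.

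**What 22 completers can resolve for one pair**
- Detectable correlation: tanh((1.960 + 0.842)/√(22 − 3)) = tanh(0.643) = 0.57.
- 95% interval for an observed r of 0.3: tanh(0.3095 ± 1.96/√19) = tanh(0.3095 ± 0.4497), or −0.14 to 0.64.

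**Does the premise hold?** The 27% to 50% requires three things together: a 5% level for each test, 22 separate tests, and a rule that any one positive supports the hypothesis. The protocol states none of them. The last is only one reading of the and/or wording in Aim 2. Against that reading stand the explicit absence of a primary outcome, the design label of a cohort study with physiological end-points, and the closing paragraph under Publication Policy, which presents the results as a source of hypotheses for later trials.

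**The case for a change.** The strongest case for a change is that the protocol itself, and not just a missing analysis plan, declares that there is no primary outcome. An analysis plan that named a deciding result would then sit oddly with the protocol. Nowhere is Aim 2 called exploratory, and the same closing paragraph also speaks of identifying contributing factors and enabling treatment strategies, which is more than exploratory language. The remedy looks cheap: soften one verb, or name one pair. It is also true that having no primary outcome does not prevent a precision statement, since the minimum of 22 completers is enough to compute one, as shown above.

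Much of this stands as description. The verb in Aim 2 is stronger than the design supports, and a precision sentence would be good practice. It does not amount to a needed change. Softening the verb, or adding the sentence, leaves every biopsy, assay, analysis and estimate as it is. Naming a principal index would have substance, but the documents give no ground for preferring one index over another. How correlations are computed, ordered and adjusted is commonly settled in an analysis plan, which may exist here. Forcing a single principal index on a broad mechanistic study also has a cost, because the joint pattern across respiration, membrane potential and network structure is what the investigators want to see.

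**Conclusion.** The mismatch is real but confined to wording: one aim speaks of a test in a study that openly has no primary outcome, no power claim and no confirmatory decision rule. If about 22 correlations were each tested at 5% and any one counted, the false-positive chance would be about 27% to 50%, assuming 22 completers, inter-index correlations of 0.5 to 0.8 and a mass–power correlation of 0.5 to 0.8. Since the protocol commits to no such rule, that figure is a caution for whoever interprets the results, not a property of the plan. A competent analyst would read the Aim 2 correlations as exploratory and judge each by its estimate and interval. No change clearly improves what the study does or can conclude, so none is asked for.
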